A considerable volume of work has also been conducted to characterize the fluctuations of the VMB across the menstrual cycle. While some studies (both culture-dependent and culture-independent) have reported no change in community composition across the menstrual cycle [Sautter 1980, Wilks 1987, Gajer 2012, Hickey 2013], others have reported varying relative abundances of aerobic and anaerobic bacteria across the cycle [Bartlett 1977] or a greater proportion of non-*Lactobacillus* species during menses [Priestley 1997, Eschenbach 2000, Srinivasan 2010, Lopes 2011, Gajer 2012, Hickey 2013]. In light of these findings, in particular those of Gajer et al. (2012) and Hickey et al. (2013), it is currently thought that the degree and type of VMB fluctuation seen across the menstrual cycle varies between women [Lopes 2011, Chaban 2014]. Further, the increased abundance of non-*Lactobacilli* species seen during menses is of particular interest given the changes to vaginal innate immune cell presence [Hill 1992], temperature [Hill 2010], oxygen and carbon dioxide concentrations [Hill 2005], and volatile fatty acid concentrations [Preti 1975] that occur during menses. These changes alter the growth conditions present in the vagina, and as such, may promote the growth of certain bacterial species over others. Given that non-*Lactobacilli* species are often present in greater abundance during menses, it is possible that the conditions of the vagina during menses could promote their growth and potentially shift a *Lactobacilli*-dominated VMB to a diverse VMB and promote BV. Moreover, the changes to vaginal temperature, dissolved gas concentrations, and volatile fatty acid concentrations that occur during menses have been shown to be exacerbated by tampon use [Preti 1975, Hill 2005, Hill 2010], suggesting that tampon use may compound any VMB changes that occur during menses.

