- Justification for choice of tampons A and B: The primary structural difference between Tampax® Pearl® Regular Tampons and Playtex® Gentle Glide® 360°® Regular Tampons is that, once inserted into the vagina, Tampax® Pearl® Regular Tampons expand axially into a rectangular prism-like shape (Fig. 2C), while Playtex® Gentle Glide® 360°® Regular Tampons expand radially into a cone-like shape (Fig. 3C). The radial expansion of the Playtex® Gentle Glide® 360°® Regular Tampons likely results in increased surface area of the tampon that is in contact with the vaginal epithelium as compared to the Tampax® Pearl® Regular Tampons. This may allow for increased absorption of menses by the Playtex® Gentle Glide® 360°® Regular Tampons as compared to the Tampax® Pearl® Regular Tampons, resulting in differing growth conditions in the vagina during

Playtex® Gentle Glide® 360°® Regular Tampon use and Tampax® Pearl® Regular Tampon use. Both tampons are inserted with a plastic applicator, and both are made of a cotton/rayon blend. The only other substantial structural difference between the two is that the Tampax® Pearl® Regular Tampons have a braided string (Fig. 2B) while the Playtex® Gentle Glide® 360°® Regular Tampons have a straight, 2 strand string (Fig 3A). Tampax® Pearl® reports that the braided string is designed to stop tampon leaks, and that it can hold up to 12 drops of fluid in addition to the volume held by the tampon (Fig. 2D). We do not anticipate this difference to substantially alter the growth conditions in the vagina because any contact between the string (braided or not) and the vaginal epithelium will be much less than that between the actual tampon and the vaginal epithelium. Another reason for choosing these tampons is that, for the past 6 years (2011-2016), Tampax® and Playtex® brand tampons have been the two most used tampon brands in the US [Experian 2016]. Examining how these tampon brands impact VMB composition will increase the generalizability of the study findings, as compared to if we selected other tampon brands.

- Pad: Always® Infinity® Regular Pads with wings (Fig. 4)
 - <http://always.com/en-us/shop-products/menstrual-pads/infinity-pads-with-flexfoam/always-infinity-regular-pads-with-wings>
 - \$0.31 per pad on amazon prime; 4.4 stars
 - $2 \text{ pads/day} * 12 \text{ days} = 24 \text{ pads} * 20 \text{ subjects} = 480 \text{ pads} *$
 $\$0.31/\text{pad} = \148.80

Figure 4: Always® Infinity® Regular Pads with wings.

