- Distribution: Subjects will receive their study tampons and pads during their enrollment meeting.
- We will instruct subjects to use the study tampons as they normally would, not wear a tampon for more than 8 hours, not wear more than one tampon at a time, contact a doctor if they experience any serious adverse effects related to tampon use including TSS symptoms, remove the tampon prior to collecting a swab during menses, and use the pads in addition to the tampons if they so choose.

- We will provide subjects with written instructions from the tampon manufacturer on tampon use and ways to minimize risk of TSS.

Self-Collected Vaginal Swabs

- As in our pilot study, a double-headed, dry, rayon swab (Starplex Scientific, Inc., S09D) will be used for sample collection (HUM00098494).
- Swab distribution: Subjects will receive their vaginal swabs for the duration of the study (assumed duration of 15 weeks) during their enrollment meeting. If additional swabs are needed, subjects will pick them up from the first floor of MSRB1.
- Swab collection: Subjects will drop off their self-collected vaginal swabs on the first floor of MSRB1 during designated time windows each week; swabs will be stored in -80°C until analysis.
- Swabbing procedure: All swabs will include the following written instructions for self-collecting the vaginal swab (HUM00098494, HUM00086661):
 1. Read these instructions before starting.
 2. Locate a sterile swab labeled with your study ID number
 3. Write today's date (the day you used the swab) in the space provided on the swab label. Complete the short survey included with the swab. It is OK to collect a sample if you are menstruating, but if you are currently using a tampon, remove it before using the swab.
 4. Wash your hands.
 5. Remove the sterile swabs from the tube. Do not let them touch your body or any surface.
 6. Gently part your labia and insert both swabs approximately 2 inches into your vagina, imagining that you are pointing it towards your lower back.
 7. Gently turn the swabs 4 times, rotating the swab about 90 degrees with each turn.
 8. Remove the swabs taking care to not touch anywhere on your body.
 9. Place both swabs back into the tube.
 10. Place the tube into the plastic bag. Wash your hands.
 11. Return the swab to the first floor of MSRB1 during one of the designated time windows this week.

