- Covariate data collection with each swab: We will provide a short survey with each swab on which subjects will record whether the swab was collected during menses as well as any changes in sexual activity, hygiene, medication use, general health, vaginal health, contraception use, pregnancy, menses since the baseline study or prior swab.
- We will remind subjects to collect swabs with twice-weekly text messages, emails, or phone calls based on preference.

Whole Community Analysis & Statistics

- DNA will be isolated from vaginal swab samples using a PowerMag Soil DNA isolation kit (Mo Bio Laboratories, Inc.) and an epMotion robot (Eppendorf epMotion 5075). The DNA samples will be submitted to the University of Michigan

Center for Microbial Systems Laboratory for amplification and sequencing of the V4 region of the 16S rRNA gene. The V4 region of the bacterial 16S rRNA gene will be amplified using dual-indexing sequencing strategy and sequenced on the Illumina MiSeq platform as described by Kozich et al. and Seekatz et al. After sequencing is completed, the 16S rRNA gene sequences will be processed and analyzed using the mothur software (version 1.34.3) and MiSeq SOP (http://www.mothur.org/wiki/MiSeq_SOP). Following sequence processing and alignment to the SILVA reference alignment [Preusse 2007], sequences will be binned into operational taxonomic units (OTUs) of 97% sequence identity. In our preliminary studies, we were able to detect and distinguish 6 different types of *Lactobacillus* among the top OTUs (>2% in at least 1 sample) from vaginal swab samples using an OTU definition of 3% sequence difference with sequences from the V4 region of the 16S rRNA gene. Relative abundances of OTUs will be calculated and we will test the dependence of within subject θ_{YC} distances on expanded tampon shape using Mann-Whitney tests or Kruskal-Wallis test, as dictated by the number of comparisons. Principal components analysis (PCoA) will be used to visualize θ_{YC} distances between samples within subjects. The same analysis protocol was used in our previous studies (HUM00098494, HUM00086661).

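### Whether a menses swab follows tampon removal or a tampon-free interval is neither fixed nor among the items listed for recording, which adds noise to the exploratory during-menses comparison and leaves one alternative to the shape explanation uncheckable

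*Combined protocol and SAP*

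**What the plan says.** All references are to the combined protocol and SAP.

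- **Sampling rule.** Under Methods – Self-Collected Vaginal Swabs, step 3 permits a swab during menstruation and adds "if you are currently using a tampon, remove it before using the swab". Menstrual Products repeats the rule: participants are to "remove the tampon prior to collecting a swab during menses". Both fix the order, removal then swab. Neither sets an interval, and neither requires that a tampon was in place.
- **Wear.** Participants are told to "use the study tampons as they normally would, not wear a tampon for more than 8 hours" and may "use the pads in addition to the tampons if they so choose". Tampon-free hours during menses are therefore permitted.
- **What is recorded.** The swab label takes a date, with no clock time. With each swab, "subjects will record whether the swab was collected during menses", together with changes in sexual activity, hygiene, medication, health, contraception, pregnancy and menses. No listed item covers tampon in place, time since removal or pad use. The baseline survey (Study Design) asks about habitual product use only.
- **Why the environment may differ.** Background says that changes in vaginal temperature, gases and fatty acids during menses "have been shown to be exacerbated by tampon use". The product justification says that the radial expansion of one product "likely results in increased surface area of the tampon that is in contact with the vaginal epithelium" and may increase absorption.
- **Analysis.** Whole Community Analysis & Statistics plans rank tests of within-subject θYC distances by tampon shape, with no term for sampling state. It treats exposure as constant within each window and reads an association as a causal effect of shape.

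**The concern.** On the plan's own rationale, a tampon changes the environment that the swab samples. A swab taken at removal and one taken some hours later may then not be equivalent measurements. Randomised order does not balance this, because the participant settles the state after assignment, swab by swab. Averaging helps little, because each product's menses contributes so few swabs. The comparison at stake is Hypothesis 1, which is exploratory but is the one for which the two products were chosen. If a product contrast appears, the investigators will want to attribute it to shape. Without a record of sampling state, they could not show whether state differed between the products, and this cannot be reliably reconstructed afterwards.

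**Working it through.** The documents give no power, alpha, effect size or variance, so there is no figure of that kind to reproduce. The one schedule figure does reproduce: 2 swabs per week × 4 weeks = 8 per cycle, as in Study Design.

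**1. Menses swabs per product.** Inputs: twice-weekly sampling (Study Design); menses of at least 4 days (Recruitment, inclusion criteria); 6 days, as used in the tampon supply calculation (Menstrual Products). Expected number = 2 × days / 7:
- 4 days: 8/7 = 1.14
- 5 days: 10/7 = 1.43
- 6 days: 12/7 = 1.71

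With an assumed alternating 3- and 4-day spacing, the count is always 1 or 2, whatever day menses starts.

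**2. Mismatched pairs.** Assume one menses swab per product, a common share p taken at removal that is the same for both products, and independent states. The probability that a woman's two swabs differ in state is 2p(1−p). For the 20 women to be enrolled (Recruitment):
- p = 0.5: 50%, 20 × 0.50 = 10 women
- p = 0.7: 42%, 20 × 0.42 = 8.4 women
- p = 0.9: 18%, 20 × 0.18 = 3.6 women

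**3. Stable habits lower this.** If p varies between women with mean p̄, the expected share is 2p̄(1−p̄) − 2Var(p). As an assumed example, take half the women at p = 1 and half at p = 0.4. Then p̄ = 0.7 and Var(p) = 0.09, so the share is 0.42 − 0.18 = 24%. The figures in step 2 are therefore upper values for a given average p, as long as p is the same for both products.

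**4. Effect on a comparison (illustration).** Let b be the shift due to state, in within-woman SD units per swab, and let pA and pB be the shares at removal under each product. For a signed paired difference with one swab per cycle:
- spurious contrast = b(pA − pB)
- variance = 2 + b²[pA(1−pA) + pB(1−pB)]

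If state is unrelated to product and p = 0.5, the spurious contrast is zero. The variance is 2 + 0.25 × 0.5 = 2.125 at b = 0.5 (about 6% more than 2) and 2 + 1 × 0.5 = 2.5 at b = 1 (25% more).

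If the shares differ by product (centred on 0.5, n = 20, two-sided 5% normal approximation), then with no true shape effect:

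| pA − pB | b = 0.5: contrast, rejection | b = 1: contrast, rejection |
|---|---|---|
| 0 | 0, 5.0% | 0, 5.0% |
| 0.1 | 0.05 SD, 5.3% | 0.10 SD, 5.9% |
| 0.2 | 0.10 SD, 6.1% | 0.20 SD, 8.8% |
| 0.3 | 0.15 SD, 7.5% | 0.30 SD, 13.7% |

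All values of b and p, and the 5% level, are assumptions. This is not the plan's rank test on θYC distances, so it indicates order of size only.

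**The case against.** A reader might infer that the during-menses comparison is biased. The documents do not support that. Bias needs the sampling state to differ by product. The expected difference in absorption makes this conceivable but does not show it; otherwise the result is noise, and the error rate stays at 5%. Nor does any section say that composition shifts in the hours after removal. That step is extrapolated from statements about temperature, gases, fatty acids and contact area.

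A reader might also infer that half the women will have mismatched swabs. That is a ceiling at p = 0.5. Pads are offered as an addition to tampons, and the supply of 4 tampons a day at the 8-hour limit (4 × 8 = 32 hours) could cover a whole day. This does not prove continuous wear, but it is compatible with a high p and few mismatches.

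Two further points stand. The survey form is not in the documents, so absence of the item rests on the description of its contents. And under an as-assigned analysis with normal wear, a product that is worn longer carries that difference as part of the effect of assignment. It becomes a problem only because the plan attributes the contrast to shape.

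What the objection does not answer is that the state is left open, is not listed for recording, and is hard to recover later.

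**Conclusion.** The point holds as a cheap improvement to data collection. Sampling state during menses is uncontrolled and, on the described survey content, unrecorded, for a comparison resting on about one or two swabs per product. The certain consequence is limited: if state affects composition, it adds noise. The conditional consequence is that, if state also differs by product, a contrast attributed to shape has a rival explanation that the data cannot test.

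The size is unknown. Mismatch is at most 18% to 50% of women for p between 0.9 and 0.5, and less with stable habits. In the illustration, the rejection rate moves from 5% to between 5.3% and 13.7%, and reaches the top of that range only with an assumed 1 SD state effect and a 30-point product difference.

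It would be tempting to extend this to the primary and secondary outcomes. The documents do not support that: those are changes from baseline to the end of each cycle, and nothing says that menses swabs determine them. Only Hypothesis 1 is clearly affected.

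**What to change.** 1. Add to the collection-day survey, for menses swabs: *Tampon in place just before this swab? Yes/no. If no, hours since the last tampon was removed.*
2. Add to step 3 a request that, where possible, menses swabs in both assigned cycles be taken at the same point relative to tampon removal, for example at a routine change. Wear habits and the existing wear instructions stay as they are.
3. Keep the comparison of all menses swabs, as assigned, as the main during-menses analysis. Report a same-state or state-adjusted comparison as a sensitivity analysis. Same-state pairs should not become the main analysis: state is chosen by the participant after assignment, so restricting to such pairs risks selection, and at p = 0.5 it would drop about 10 of the 20 women.
4. Tabulate sampling state by product, so that a reader can see whether it differed.

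The cost is one or two survey items on a form already completed at each swab, one sentence in step 3, and slightly less freedom over when to swab.

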We propose a longitudinal, interventional, case-crossover study design to examine whether expanded tampon shape affects VMB composition during, and in between menses. We will recruit 20 women from the University of Michigan, Ann Arbor to use Tampax® Pearl® Regular Tampons (expand into a rectangular prism-like shape) and Playtex® Gentle Glide® 360°® Regular Tampons (expand into a conical shape) for one menstrual cycle each, in a randomly assigned order. We will obtain twice-weekly self-collected vaginal swabs for a 2-3 week baseline window before the first menstrual cycle with an assigned tampon, followed by the two menstrual cycles with assigned tampon use, and finishing with one menstrual cycle with menstrual product use according to each subject's normal habits. DNA will be isolated from the vaginal swabs, and the bacterial 16S rRNA encoding genes will be amplified by PCR. Sequencing will be performed using the MiSeq Illumina platform, and analyzed to answer the above questions.

Outcomes and aims

- Primary Outcome: Change in relative abundance of *Lactobacillus* species from: baseline to the end of first menstrual cycle, baseline to the end of second menstrual cycle, and baseline to the end of third menstrual cycle (approximately 14 weeks)
- Secondary Outcome: Change in relative abundance of *Gardnerella vaginalis* from: baseline to the end of first menstrual cycle, baseline to the end of second menstrual cycle, and baseline to the end of third menstrual cycle (approximately 14 weeks)
- Exploratory Outcomes
 - To characterize intra-woman, during-menses changes in VMB composition caused by (see Methods – Study Design and Methods – Whole Community Analysis & Statistics sections for notes on causal inference) changing the expanded tampon shape of tampon used.
 - Hypothesis 1: VMB composition will vary between menses with Tampax® Pearl® Regular Tampon use and Playtex® Gentle Glide® 360°® Regular

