Tampon use because the different expanded shapes of the two tampons will alter the vaginal environment differently and thus promote growth of different taxonomic groups. The primary structural difference between Tampax® Pearl® Regular Tampons and Playtex® Gentle Glide® 360°® Regular Tampons is that, once inserted into the vagina, Tampax® Pearl® Regular Tampons expand axially into a rectangular prism-like shape, while Playtex® Gentle Glide® 360°® Regular Tampons expand radially into a conical shape. The radial expansion of the Playtex® Gentle Glide® 360°® Regular Tampons likely results in increased surface area of the tampon that is in contact with the vaginal epithelium as compared to the Tampax® Pearl® Regular Tampons. This may allow for increased absorption of menses by the Playtex® Gentle Glide® 360°® Regular Tampons as compared to the Tampax® Pearl® Regular Tampons, resulting in differing growth conditions in the vagina during Playtex® Gentle Glide® 360°® Regular Tampon use and Tampax® Pearl® Regular Tampon use.

- To characterize intra-woman, between-menses changes in VMB composition caused by (see Methods – Study Design and Methods – Whole Community Analysis & Statistics sections for notes on causal inference) changing the expanded shape of tampon used.
 - Hypothesis 2.1: Persistence of VMB changes observed during menses caused by changing the expanded shape of the tampon used will vary dependent on baseline VMB community type such that VMB changes will persist for greater time between menses in women with typically diverse VMB that confer reduced colonization resistance compared to a *Lactobacilli* dominated VMB [Borovkova 2011, Lopes 2011, Borges 2014, reviewed in Hickey 2012].
 - Hypothesis 2.2: Within women with *Lactobacilli* dominated baseline VMB, persistence of VMB changes observed during menses caused by changing expanded tampon shape will vary based on the degree of reduction of *Lactobacilli* abundance during menses such that changes resulting in greater reductions of *Lactobacilli* abundance will persist for greater time between menses.

Methods

Recruitment

- We will recruit 40 women from the University of Michigan, Ann Arbor during the Winter 2017 semester.
 - We will make an in-person announcement in Women’s Studies 400: Women’s Reproductive Health (taught by [name], Dept. of OB/GYN) according to the following script:

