- Exclusion criteria: Respondents will be excluded if they are pregnant or are planning on becoming pregnant during the study; have difficulty using tampons; currently have, or have had TSS; currently have an STI; currently have a UTI; are currently using current antibiotics, or used antibiotics within 4 weeks prior to enrollment; are currently using current antifungals, or used antifungals within 4 weeks prior to enrollment; or have an autoimmune condition.

Study Design

- This study will be a longitudinal, interventional, case-crossover study with three exposure levels:
 - Experimental exposure levels: Each subject will use Tampax® Pearl® Regular Tampons and Playtex® Gentle Glide® 360°® Regular Tampons for one menstrual cycle each, in a randomly assigned order.
 - Control exposure level: Each subject will use menstrual products according to their normal habits for a third menstrual cycle.
 - A case-crossover design ensures exchangeability between treatment windows within each subject for all time invariant characteristics. Under exchangeability and the assumptions of an intent-to-treat analysis (covered in Methods – Whole Community Analysis &

Statistics), the actual outcome observed under one treatment for an individual equals the counterfactual outcome under that treatment for that individual, so association between expanded tampon shape and VMB composition represents a causal relationship. This study design and the intent-to-treat analytic strategy will allow us to make causal inference in reference to the effect of expanded tampon shape on VMB composition.

- Vaginal swabs will be self-collected by each subject twice weekly for four different exposure windows (Fig. 1):
 - A 2-3 week baseline window after the last menstrual period prior to enrollment; 4-6 baseline samples per subject.
 - One menstrual cycle using the Tampax® Pearl® Regular Tampons; 8 samples.
 - One menstrual cycle using Playtex® Gentle Glide® 360°® Regular Tampons; 8 samples.
 - The final menstrual cycle with menstrual product use according to the subject's normal habits; 8 samples for the subject's normal habits.

[figure not shown]

Figure 1: Study design.

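### The theta-YC comparison states no unit of analysis and names independent-sample rank tests for a crossover, so the matching goes unused and the direction of error is open

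*Combined protocol and SAP*

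**What the plan says.** Methods, Whole Community Analysis & Statistics, tests whether within-subject theta-YC distances depend on shape: "distances on expanded tampon shape using Mann-Whitney tests or Kruskal-Wallis test, as dictated by the number of comparisons". The number of comparisons is the only stated basis for choosing the test. The section does not say which swab pairs supply the distances, what the reference is (baseline, previous swab or other cycle), whether distances are summarised per woman and cycle, or whether women are pooled or tested singly. The nearest text concerns the ordination plot, which will show "distances between samples within subjects". The section also says "The same analysis protocol was used in our previous studies (HUM00098494, HUM00086661"), without describing what those studies did.

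Under Study Design, each woman uses the two tampons "for one menstrual cycle each, in a randomly assigned order". Swabs are twice weekly: "One menstrual cycle using the Tampax® Pearl® Regular Tampons; 8 samples", and the same number for Playtex. After that, "Each subject will use menstrual products according to their normal habits for a third menstrual cycle".

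The tests serve two exploratory aims under Outcomes and aims: "To characterize intra-woman, during-menses changes in VMB composition caused by" a change in expanded shape, and "To characterize intra-woman, between-menses changes in VMB composition caused by" the same change. No paired, blocked, clustered or mixed-model method appears anywhere. Study Design and the intent-to-treat paragraph rest causal inference on exchangeability within each woman.

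**The concern.** Mann-Whitney and Kruskal-Wallis compare groups of independent observations. Grouped by shape, this study has none. Each woman is in every group, her swabs form a short time series, and distances that share a swab are linked. The within-woman comparison that justifies the crossover plays no part in either test.

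These are the only inferential tests the document names, and the aims they serve are worded causally. With the unit left open, the same swabs could be significant under one unit and not under another, and nothing in the plan says which analysis was intended.

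**Working it through.** **Inputs from the documents.** 20 women (Recruitment enrols the first 20 eligible, though it also speaks of recruiting 40; 20 is used here). 4 to 6 baseline swabs and 8 per cycle over three cycles (Study Design). Menses of at least 4 days (inclusion criteria), with tampons supplied for 6 days (Menstrual Products). The swab count is consistent: 4 + 3×8 = 28 to 6 + 3×8 = 30, against 30 issued and 15 weeks × 2 = 30. The documents give no alpha, variance, correlation or power, so there is no inferential figure to reproduce.

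**Observations per product, by unit.**
- Per-woman summary: 20, matched to the same 20 women on the other product.
- Swabs: 20 × 8 = 160.
- Within-cycle pairs: 8×7/2 = 28 per woman, 560 pooled.
- Baseline-by-cycle pairs: 4×8 = 32 to 6×8 = 48 per woman, 640 to 960 pooled.
- Menses swabs per cycle: 4×2/7 = 1.1 to 6×2/7 = 1.7, so 1 or 2 per woman.

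**Cost of ignoring the matching.** With one value per woman per product, the mean difference has variance 2σ²(1−ρ)/20. An independent-sample test takes it as 2σ²/20. At ρ = 0.6 the true variance is 0.4 of what is assumed, so the test is conservative. At ρ = 0 the two agree. Simulation of 20 normal pairs (20,000 runs, two-sided 5%):

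| ρ (assumed) | Mann-Whitney, null | Signed-rank, null | Mann-Whitney power, 0.5 SD | Signed-rank power, 0.5 SD |
|---|---|---|---|---|
| 0 | 5.0% | 4.8% to 5.1% | 32% | 31% |
| 0.3 | 2.0% | 4.8% to 5.1% | 29% | 41% |
| 0.6 | 0.5% | 4.8% to 5.1% | 26% | 64% |

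**Effect of the unit.** Theta-YC = 1 − Σpq / (Σ(p−q)² + Σpq), computed on simulated communities. Assumed: 20 women, 5 baseline swabs, 8 per cycle with 1 or 2 in menses, 4 taxa with logit means 2, 0, 0, 0, between-woman SD 1 or 2, woman-by-period SD 0, 0.35 or 0.7, swab SD 1. That gives 2×2×3 = 12 null settings. The main run used 2,000 trials per setting (Monte Carlo SE at most 1.1 points). Where runs of this model differed, the widest range is shown.

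| Unit | Test | Null rejection at 5% |
|---|---|---|
| One median menses-to-baseline distance per woman | Mann-Whitney | 0.1% to 2.0% |
| Same, three cycles | Kruskal-Wallis | 0.0% to 1.0% |
| Same, two products | Signed-rank | 4.1% to 5.6% |
| Cycle 1 minus cycle 2 difference, by randomised order | Mann-Whitney | 3.6% to 5.2% |
| One distance per menses swab, women pooled | Mann-Whitney | 0.0% to 3.2% |
| All menses-to-baseline pairs, women pooled | Mann-Whitney | 5% to 21% |
| Same, three cycles | Kruskal-Wallis | 5% to 28% |
| All within-cycle pairs, 560 vs 560 | Mann-Whitney | 17% to 45% |
| One woman, menses-to-baseline pairs | Mann-Whitney | 12% to 25% |
| One woman, within-cycle pairs, 28 vs 28 | Mann-Whitney | 29% to 50% |
| One woman, 8 vs 8 swabs, woman-by-period SD 0 | Mann-Whitney | 2.8% to 5.2% |
| One woman, 8 vs 8 swabs, woman-by-period SD 0.7 | Mann-Whitney | 20% to 24% |

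With one distance per menses swab and 2 swabs per product in one woman, the smallest exact two-sided p-value is 2/6 = 0.33, so that test cannot reach significance at all.

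**A second model** (8 taxa, swab autocorrelation 0 to 0.5, cycle SD 0 to 1, all 8 cycle swabs used) gave the same pattern. Per-woman Mann-Whitney rejected 0.0% to 0.8%, and signed-rank 4.9% to 5.3%. One distance per swab, pooled, went either way: 0.3% to 22%. Pooled baseline pairs rejected 7% to 51%, and within-cycle pairs 22% to 45%. One woman's 8 vs 8 swabs gave 4.2% with independent swabs and no cycle variation, otherwise 13% to 36%.

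**Power in the first model.** One product shifts one taxon by 1.5 logits or raises swab SD 1.5-fold. On per-woman summaries, Mann-Whitney had 2% to 22% power against 10% to 46% for signed-rank with 2 menses swabs, and 2.5% to 10.5% against 9% to 24% with 1. Signed-rank was higher in all 24 alternatives.

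**The case against.** The aims are labelled exploratory, the two earlier studies may define the unit, and every rate above rests on assumed variances. A test inside each woman is a fair reading of the intra-woman wording, and then there is no cross-woman pairing to lose. The causal claim is argued from exchangeability and assumed compliance, not from the choice of test. All of this stands as a limit on weight. It does not supply the unit or make the named tests use the matching. The single-woman reading meets a separate difficulty: each woman has one cycle per product, so product cannot be separated from cycle.

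A reader might infer more than the documents support:
- That the tests inflate false positives in general. They do not: per-woman summaries and pooled menses swabs are conservative in these simulations. Inflation comes mainly from counting swab pairs as independent, and even there the lowest pooled menses-to-baseline rate was 5.3%.
- That no use of these tests is valid. Mann-Whitney on cycle differences between the randomised orders held its level, though the plan does not describe it. There is also no penalty for per-woman summaries at zero correlation, and one woman's 8 vs 8 test is near nominal if her swabs are independent and her cycles do not vary by chance.
- That two analysts could reach opposite conclusions about direction. In 12,000 simulated null trials, pooled-pair Mann-Whitney and per-woman signed-rank were never both significant in opposite directions. Significant under one and not under the other is the most that can be said.
- That the *Lactobacillus* or *Gardnerella* outcomes are affected. No test is named for them, so this point does not reach them.

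**Conclusion.** The point holds. The unit is not stated here, and the named tests, grouped by shape, do not use the within-woman matching on which the causal claim depends. Those two statements follow from the text alone. The size and direction of error do not: they depend on the unit and on unknown variances and correlations. In the first model, null rejection at nominal 5% runs from about 0% to 3% for the per-woman and pooled menses-swab units to as much as 45% for pooled within-cycle pairs. For per-woman summaries the cost is power, and it grows with the correlation between a woman's two values (simulated Spearman 0.36 to 0.66 in the first model; not given in the documents). The consequence is confined to the exploratory community aims, but it should be settled before analysis.

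**What to change.** In Whole Community Analysis & Statistics:
- Define one theta-YC summary per woman per product for each aim. During menses this could be the median distance of her menses swabs from her baseline swabs; between menses, the same for non-menses swabs.
- Compare Tampax with Playtex by Wilcoxon signed-rank, or by Mann-Whitney on cycle 1 minus cycle 2 differences between the two randomised orders, which also allows for a period effect.
- If the normal-habits cycle is included, replace Kruskal-Wallis with Friedman or a mixed model with woman as a random effect. Report it descriptively, because that cycle is always third.
- State that distance from baseline measures the size of a shift and not its direction: two products could move communities equally far in different directions and show no difference. For Hypothesis 1, a permutation test of community composition that swaps product labels within woman can be added.
- Show single-woman results descriptively, without p-values.

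The cost is a few sentences and a few lines of code, with no new data. Results become per-woman summaries instead of per-swab comparisons. Power with 20 women remains low: 9% to 46% for signed-rank in the alternatives tried.
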